11.7 Unscheduled Visits

Subjects may come for additional unscheduled office visits if necessary. Circumstances that may warrant additional visits include but are not limited to:

- RA-related AEs requiring medical evaluation
- Device deficiency evaluation; and/or
- Device dose adjustment, suspending stimulation, resuming stimulation or implant decommissioning.

Unscheduled visits are related to the study and not standard of care. Prescription refill visits are not considered unscheduled visits. Information gathered during an Unscheduled visit must be recorded and entered into the study database on the appropriate CRF.

11.8 Suspending and Resuming Stimulation

Stimulation must be suspended before an MRI, prior to an elective surgical procedure, or if there is a concern of subject's safety.

Additionally, stimulation may be suspended at any time after completion of Week 12 assessments at the discretion of the clinical investigator and the subject. The clinical investigator and subject may decide to suspend stimulation in the event the subject experiences worsening of RA symptoms or if the subject does not experience adequate clinical improvement and continuation of stimulation is deemed not in the best interest of the subject (e.g., subject experiences AE that is definitely or probably related to stimulation). RA disease activity is assessed and documented at all follow-up visits. Results from these assessments may be used to guide decision-making.

MicroRegulator should be fully charged prior to suspending stimulation. Stimulation from MicroRegulator can be suspended by Prescription Pad as detailed under "Suspending Therapy" section of the SetPoint System IFU Prescriber Manual. Pink visual indicator on Energizer confirms therapy suspension. Stimulation will no longer be delivered until therapy is resumed. Subjects should continue to follow the regular visit schedule, adhere to all study procedures and be monitored for safety while therapy is suspended.

If the clinical investigator and subject decide to resume stimulation (examples include, but are not limited to, following resolution of AE, after MRI, after elective procedure), stimulation from MicroRegulator can be resumed by Prescription Pad as detailed under "Resuming Therapy" section of the SetPoint System IFU Prescriber Manual. Green or orange visual indicator on Energizer confirms that therapy has been resumed.

11.9 Implant Decommissioning

Implant battery charge level will be monitored by the designated research coordinator at every follow-up visit. If a charge level of less than 75% is observed, the subject will be counseled on the importance of charging their implant on a weekly basis and be reminded that their implant will be decommissioned in the event the subject does not comply. Once fully discharged, the battery cannot be recharged, and automatic delivery of stimulation will no longer occur. In this case, the MicroRegulator must be decommissioned (permanently turned off) and the subject must return all external equipment (Energizer and Wireless Charger). Contact SetPoint Medical to request placement of the MicroRegulator in decommission mode. If a subject wants or needs to have their implant permanently turned off and left in place at the end of the study or earlier, the implant will be decommissioned in accordance with the SetPoint System Instructions for Use Prescriber Manual. The subject would be required to return their Energizer and visit the site at least 24 hours following the initiation of decommissioning, to ensure that the decommissioning process occurred as expected.

Subjects that have their implant decommissioned prior to Week 264 and remain in the study should continue to follow the regular visit schedule, adhere to all study procedures and be

CONFIDENTIAL

May not be reproduced outside of SetPoint Medical without written permission from Document Control.

62 of 111

monitored for safety. Subjects choosing to end participation after implant decommissioning will be asked to contact the clinical investigator in the event they experience any safety issue related to the investigational implant.

If a device failure precludes decommissioning, the subject will be followed for safety for a period of 10 months, at which point the internal battery would be fully depleted. If the 10-month period has not elapsed at the point the subject exits the study, investigator agrees to follow subject under their standard of care. In this case, follow-up will constitute documented contact with the subject once every 2 months, along with documentation of any reported AEs. Subjects will be informed about the risks associated with attempting to recharge a device that has a completely depleted battery.

11.10 Explant Procedure

If a subject wants or needs to have their implant removed at the end of the study or earlier, this must be communicated to the study sponsor prior to scheduling or performing the explant procedure. Before the explant procedure, MicroRegulator stimulation must be suspended (see Section 11.8). The surgical investigator will perform pre-surgical clearance testing per standard of care. The surgical investigator will remove the implant according to the explant procedure protocol outlined in SetPoint System Instructions for Use Surgeon Manual. In the event an implant cannot be explanted, it will be decommissioned. In the unlikely event that a failed implant cannot be explanted, and the nature of device failure precludes decommissioning, the subjects will be followed for safety for a period of 10 months, at which point the internal battery would be fully depleted. (see Section 11.9).

The explanted MicroRegulator and POD shall be returned to SetPoint Medical according to the return shipping instructions provided or disposed according to investigator's institutional procedures for disposal of blood contaminated medical devices. Following the explant procedure, subjects will be evaluated to assess for proper wound healing and post-op recovery per standard of care. Once the subject is cleared post-surgery, the subject will exit the study. Any AE resulting from the explant procedure should be followed to resolution.

11.11 Duration of Study Period

The study duration is approximately 84 months (8 months for enrollment into Stage 1, 6 months for a pause in enrollment after Stage 1, 12 months for enrollment into Stage 2, and approximately 58 months for completion of follow-up).

For a given subject, the maximum study duration is 1,899 days (about 5 years, 3 months):

- 30 days from informed consent to Implant Procedure
- 21 days between Implant Procedure and randomization at Day 0
- 84 days (about 3 months) between initiation of stimulation at Day 0 to Week 12

- 1,764 days (about 4 years, 10.5 months) between Week 12 and Week 264

A timeline of the key study visits is provided in **Figure 13**.

[figure not shown]

Figure 13: SPM-020 Study Timeline

12 STUDY PROCEDURES

12.1 Pregnancy Test and Birth Control Methods

Female subjects of childbearing potential must undergo a pregnancy test and confirm birth control method on the day of informed consent, before initiation of the implant procedure, and at each follow-up visit in accordance with Schedule of Assessments (see Section 6). Female subjects that are post-menopausal or who have documented surgical history of hysterectomy or tubal ligation are not considered to be of childbearing potential.

In case of a positive pregnancy test before Implant Procedure, the subject will be considered as a screen failure and will exit the study.

In case of a positive pregnancy test after Implant Procedure, the pregnancy will be reported as an AE, the implant must be decommissioned (see Section 11.9) and the subject followed for safety, per standard of care. Data collected up to this point will be maintained in the EDC and included in the safety analysis.

Risks associated with use of conventional synthetic DMARDs during pregnancy are identified in the labeling supplied with these drugs and should be reviewed with the subject. Leflunomide and Methotrexate should be stopped immediately in case of a positive pregnancy test, in accordance with the package labeling.

Female subjects of childbearing potential will be required to use acceptable birth control method(s) during the entire duration of the study. Acceptable methods of contraception may include:

- Established use of hormonal contraceptives (e.g., oral, injectables, vaginal ring, intra-uterine device, implant, transdermal patch);
- Non-hormonal IUD
- Double-barrier methods contraceptives (i.e., condom, diaphragm or cervical/vault caps used with spermicide (foam, gel, film, cream or suppository);

- Vasectomized male partner, if the sole partner for the subject;
- Non-sexually active female; or
- Same-sex partner.

12.2 RA Disease Activity Assessments

RA disease activity assessments are listed below and shall be performed in the order indicated:

- HAQ-DI
- SGA
- Subject's pain assessment
- TJC28
- SJC28
- EGA
- hsCRP

Refer to Section 3 for definitions of terms.

12.2.1 HAQ-DI

Subjects will complete the HAQ-DI questionnaire using a paper form.

12.2.2 SGA

Subjects will complete a global assessment of their RA disease activity using a paper form. Subjects must complete their assessments independently from Joint Evaluator's assessment.

12.2.3 Subject's Pain Assessment

Subjects will complete their assessment of the severity of their RA-related pain using a paper form.

12.2.4 TJC28 and SJC28

A total of 28 joints will be scored for presence or absence of tenderness or pain and swelling. All joint assessments will be performed by an independent, blinded Joint Evaluator with appropriate training and experience. Each subject should be assessed by the same Joint Evaluator throughout their participation in the study. The subject's Joint Evaluator *must* be the same at Screening and Week 12. Joints that have been replaced or injected with intra-articular steroids during the study are considered unevaluable.

12.2.5 EGA

After performing joint assessments, the same Joint Evaluator will conduct a global assessment of the subject's RA activity using a paper form. Each subject should be assessed by the same Joint Evaluator throughout their participation in the study. The subject's Joint Evaluator *must* be the same at Screening and Week 12. The Joint Evaluator must complete their assessments without knowledge of SGA.

12.2.6 hsCRP

Blood samples for hsCRP will be collected using sampling kits and shipped at room temperature to a central laboratory for analysis through Week 192 (see Section 12.3). Serum concentration of hsCRP (mg/L) will be determined by immunoturbidimetric assay. Blood samples for hsCRP will be analyzed locally from Week 204 through Week 264.

12.3 Clinical Laboratory Tests

Blood samples will be collected at the site and sent to a central laboratory (ICON Laboratory Services) through Week 192. Analysis will include the following according to the schedule of assessments (see Section 6):

- RF
- ACPA
- eGFR
- CBC; and
- Inflammatory biomarkers (e.g., IL-6, SAA, MMP3).

The central laboratory will provide each site with sampling kits, shipping boxes and detailed instructions on blood sample collection, preparation and shipping.

Blood samples collected at Week 204 through Week 264 will be analyzed locally. The following analytes will be tested:

- Complete blood count (CBC), platelet count, differential count

All laboratory reports shall be reviewed by the site investigator and filed in the subject binder. In the event of a clinically significant abnormality, an adverse event shall be reported and labs shall be repeated and monitored at the investigator's discretion until resolved or considered medically stable.

Samples collected for surgical clearance shall be in accordance with the site's standard of care practices and analyzed locally. Testing may include:

- Platelet count, differential count
- Serum sodium, potassium, bicarbonate, chloride, magnesium, calcium, BUN, serum creatinine
- Urinalysis; and
- PT, PTT, INR.

12.4 Hand MRI

A contrast-enhanced MRI of one hand identified by the rheumatologist to be clinically most severe will be ordered by the rheumatology site and acquired at an MRI facility that has been selected and qualified to perform this procedure.

The MRI images will be acquired before and after intravenous administration of gadolinium-based contrast to maximize sensitivity and specificity for inflammation. Instructions on image acquisition will be provided in a separate manual from the MRI central laboratory. The same hand must be imaged using the same MRI scanner and coil at Screening, Week 12, and Week 24 for a given subject. Only 1.5T and 3.0T whole-body scanners and transmit-receive (Tx/Rx) coils, ideally knee coils, are acceptable for this study. In vitro testing of MicroRegulator and POD indicates that it passes standard testing for safe use in 1.5 T and 3.0 T MRI studies. Safe scanning parameters are provided in the SetPoint Medical Surgeon, Prescriber and Patient Manuals.

The MRI images will be transmitted promptly to the MRI central laboratory for quality check, reading and quantification. If any of the images are rejected for inadequate quality, the subject shall be scheduled for a repeat MRI within 7 days from the first MRI date.

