Study Procedures	
 Enrollment. Subjects meeting all the inclusion and none of the exclusion criteria are considered enrolled once Implant Procedure is attempted. Implant Procedure. Subjects meeting final eligibility will undergo placement of the SetPoint System in the neck, on the left cervical vagus nerve within the carotid sheath. The procedure will take place in an operating room under general anesthesia and be performed by surgeons trained and experienced in procedures involving implantation of vagus nerve stimulators. Randomization. Within 14-21 days after Implant Procedure and after completing Day 0 assessments, subjects will be assigned randomly in a 1:1 ratio into either a treatment or control group using an interactive response technology. Randomization will be stratified by inadequate response or loss of response to Janus kinase inhibitors (JAKi); inadequate response or loss of response to ≥ 4 biological DMARDs (bDMARDs) with ≥ 2 mechanisms of action; and RA severity at Day 0. All subjects, investigators and site staff will remain blinded to the treatment assignment until the last subject in Stage 2 completes Week 12 follow-up assessments and the dataset for primary analysis is locked. Active & Non-active Stimulation. Through Week 12, subjects assigned to the treatment group will receive active stimulation for 1 min once per day, and those

CONFIDENTIAL

May not be reproduced outside of SetPoint Medical without written permission from Document Control.

25 of 111

[figure not shown]
	assigned to the control group will receive non-active (sham) stimulation for 1 min once per day. After completion of Week 12 assessments, all subjects in the control group will crossover to active stimulation and all subjects (treatment and control) will receive active stimulation for 1 min once per day.
Study Population	Adults (22-75 years of age, inclusive) with active, moderate to severe RA despite ongoing treatment with a conventional synthetic DMARD who have had an inadequate response, loss of response or intolerance to 1 or more biologic or targeted synthetic DMARDs, including JAKi. Note: Subjects with an inadequate response or loss of response to JAKi will be limited to 6 subjects.

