6 SCHEDULE OF ASSESSMENTS

6.1 Informed Consent to Week 12 (Primary Endpoint)

Assessment	Informed Consent & Screening (Baseline)	Enrollment & Implant Procedure (≤ 30 d post-Informed Consent)	Post-Surgical Clearance ($14-21$ d post-Implant Procedure)	Day 0 (Randomization & Initiation of Stimulation) ($14-21$ d post-Implant Procedure)	Titration 1 (7 ± 2 d ²)	Titration 2 (14 ± 2 d ²)	Titration 3 (21 ± 2 d ²)	Week 4 (28 ± 3 d ²)	Week 8 (56 ± 5 d ²)	Week 12 (Primary Endpoint & One-way Crossover) (84 ± 7 d ²)
Informed consent	X*									
Vital signs	X*			X						X
Physical exam and medical history	X*									
Pregnancy test (childbearing female)	X*	X	X	X	X	X	X	X	X	
RA disease activity assessments ¹	X*			X				X	X	X
RA prior and current medication	X*									
Energizer fit test	X*									
SF-36 & EQ-5D-5L questionnaires	X			X				X	X	X
Blood collection (RF, ACPA, eGFR)	X									
Blood collection (CBC, biomarkers)	X			X				X	X	X
Hand MRI	X									X
12-lead ECG	X									X
X-ray cervical spine	X									
Surgical clearance	X		X							
Implant procedure in operating room		X								
Randomization				X						
Subject training on the use of Energizer				X						
Device check & dose titration				X	X	X	X			X ³
Device check & dose adjustment if needed								X	X	
Blinding assessment ⁴								X		X
Treatment decision for long-term follow-up										X
Device deficiency reporting		X	X	X	X	X	X	X	X	X
Adverse event reporting	X	X	X	X	X	X	X	X	X	X
Concomitant medication	X	X	X	X	X	X	X	X	X	X

Abbreviations: ACPA, anti-citrullinated protein antibodies; CBC, complete blood count; d, day; EGA, evaluator's global assessment; eGFR: estimated glomerular filtration rate; HAQ-DI, Health Assessment Questionnaire Disability Index; hsCRP, high-sensitivity C-reactive protein; MRI, magnetic resonance imaging; RA, rheumatoid arthritis; RF, rheumatoid factor; SGA, subject's global assessment; SJC, swollen joint count; TJC, tender joint count

* Screening assessments that must be conducted on the day of informed consent to determine subject's initial eligibility and baseline values for the primary and key secondary efficacy endpoints.

¹ RA disease activity assessments include: HAQ-DI, SGA, subject's pain assessment, TJC28, SJC28, EGA, and hsCRP. Subjects must have ≥ 4 TJC28 and ≥ 4 SJC28 at consent to be eligible.

² From Day 0 (randomization).

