11.6 Follow-up

The follow-up period begins immediately post-randomization and initiation of stimulation. Each subject will return for 6 follow-up visits between Day 0 and Week 12, and 24 follow-up visits in the open-label, long-term follow-up period, starting after Week 12 assessments and continuing through Week 264 (end of study). Visits must occur within specified windows from Day 0 as detailed in Schedule of Assessments (see Section 6).

The protocol-required follow-up assessments are described in the following sections.

11.6.1 Follow-up through Week 12

The protocol-required follow-up assessments at Week 4, 8 and 12 include the following and should be performed in the order specified prior to the device check and any dose adjustment:

- Subject's, Joint Evaluator's and Co-PI Rheumatologist blinding assessment (Week 4 and 12)
- Collection of vital signs (Week 12)
- 12-lead ECG (Week 12)
- Pregnancy test for female subjects with childbearing potential and confirmation of birth control method (see Section 12.1)
- RA disease activity assessments (see Section 12.2)
- SF-36 and EQ-5D-5L questionnaires
- Blood collection for CBC and inflammatory biomarkers (see Section 12.3)
- Reporting of any AEs, device deficiencies and change in concomitant medications
- Suspending therapy before the hand MRI (Week 12; see Section 11.8)
- Hand MRI (Week 12; see Section 12.4)
- Review of clinical outcomes and discussion of treatment options for continuation in the long-term follow-up period of the study (after completing assessments at Week 12). The Co-PI Rheumatologist will review with the subject their clinical outcomes and determine which option is in the subject's best interest. The Co-PI Rheumatologist and the subject are blinded to initial treatment assignment in making this decision. The option chosen will be recorded on the follow-up visit CRF and entered into EDC. Options include:
 - Receive active stimulation
 - Receive additional RA treatment with active stimulation (see Section 14.5)
 - Receive additional RA treatment without active stimulation (i.e., stimulation is suspended, see Section 11.8) with a possibility to receive active stimulation at a later time
 - Permanently turn off (decommission) the study implant (see Section 11.9)
 - Undergo an explant procedure to surgically remove the implant (see Section 11.10)

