- Re-registration of Microregulator following MRI at Week 12. Cross-over of the control group to active stimulation by updating the prescription rule to deliver active stimulation. The prescription rule for treatment subjects will remain the same, delivering active stimulation. Re-registration will be performed by unblinded technicians at SetPoint Medical. The blind for all study roles that are blinded will be maintained (see Section 18.3).
- Device check and dose titration following MicroRegulator re-registration at Week 12, depending on the option chosen for long-term follow-up.

11.6.2 Open-label, long-term follow-up through Week 264

Protocol-required follow-up assessments at Week 24 through Week 264 are detailed below and in Schedule of Assessments (see Section 6) and should be performed in the order specified prior to the device check and any dose adjustment:

- Collection of vital signs
- 12-lead ECG (Week 24, 48, 96, 144, 192)
- Pregnancy test for female subjects with childbearing potential and confirmation of birth control method (see Section 12.1)
- RA disease activity assessments (see Section 12.2)
- SF-36 and EQ-5D-5L questionnaires (Week 24, 48, 96, 144, 192)
- Satisfaction Questionnaire (Week 24)
- Blood collection for CBC (see Section 12.3)
- Blood collection for inflammatory biomarkers (Week 24) (see Section 12.3)
- Reporting of any AEs, device deficiencies and change in concomitant medications, including the need, timing and type of additional RA treatment
- Suspending therapy before the hand MRI and resuming therapy afterwards (Week 24; see Section 11.8)
- Hand MRI (Week 24; see Section 12.4)

At Week 264, once all assessments are completed, every subject's MicroRegulator must be decommissioned (see Section 11.9).

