5.8.2 Multiple Assessments and Visits

If a variable (e.g., MRI, TJC, SJC) has been assessed multiple times at the same visit, only the last assessment will be used.

Only completed scheduled visits will be included in summary tables (**Appendix B**). Listings will include scheduled and unscheduled visits (**Appendix C**).

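### A rejected Week 12 hand MRI can be repeated after a control subject has crossed to active stimulation, and the SAP may take that repeat as the sham result

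*Protocol*

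**What the plan says.** Protocol 11.6.1 gives the Week 12 steps in a fixed order. Therapy is suspended for the hand MRI, the scan is taken, and the options for long-term follow-up are discussed. Then comes "Re-registration of Microregulator following MRI at Week 12. Cross-over of the control group to active stimulation by updating the prescription rule", followed by "Device check and dose titration following MicroRegulator re-registration at Week 12, depending on the option chosen for long-term follow-up". The trigger is the scan itself; nothing is said about its acceptance.

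Protocol 12.4 sends the images to a central MRI laboratory for quality check and reading. If any are rejected, "the subject shall be scheduled for a repeat MRI within 7 days from the first MRI date". The section makes no special provision for Week 12, the visit at which controls change treatment.

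The Protocol Summary (Section 4) is worded differently: "After completion of Week 12 assessments, all subjects in the control group will crossover to active stimulation".

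On data selection, SAP 5.8.2 states: "If a variable (e.g., MRI, TJC, SJC) has been assessed multiple times at the same visit, only the last assessment will be used". It adds that summary tables use completed scheduled visits only. The RAMRIS text in SAP 8.6.1 does not exclude a scan taken after crossover.

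**The concern.** Week 12 is the only randomised MRI comparison, because the next scan, at Week 24, comes after controls have switched. If a control scan is rejected and repeated once active stimulation has begun, the value analysed as sham is no longer a sham value. The change from sham to active falls on the control arm alone, since treated subjects' prescription rule stays the same at re-registration.

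The same scan has a second use. In the long-term SAP (CLP-008), Week 12 is the MRI baseline for the COL population (Table 14.8.2.13, Listing 16.8.2.7.8). A repeat taken after active dosing would then stand as a pre-stimulation baseline.

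**Working it through.** The plan gives no figure on this point, so there is none to reproduce. The check is of sequence, then of scale.

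**Inputs**
- Week 12 visit: day 84 ± 7, so days 77 to 91 (Protocol 6.1).
- Repeat scan: up to 7 days after the first (Protocol 12.4).
- Dose after titration: 1 minute once per day (Protocol 11.5.4).
- Stimulation is suspended before any MRI (Protocol 11.8).
- Control arm: 120 to 125 subjects (240 to 250 randomised 1:1).
- MRI rejection rate: not stated; 2% to 10% assumed.

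**Exposure before the repeat.** Let the first scan fall on day d. Assume re-registration and titration happen the same day, which is the earliest that 11.6.1 permits. The repeat may be as late as d + 7, so the longest exposure is (d + 7) − d = 7 days, or about 7 daily doses.

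| First scan (day) | Latest repeat (day) |
|---|---|
| 77 | 84 |
| 84 | 91 |
| 91 | 98 |

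If re-registration comes later than the scan day, the exposure is shorter. Because stimulation is suspended for each MRI, the repeat is taken after active dosing, not during it.

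**Which scan is analysed.** If the repeat is recorded under the Week 12 visit, SAP 5.8.2 selects it. If it is recorded as unscheduled, it stays out of the summary tables. The SAP does not say which applies. If the rejected scan is unreadable, the repeat is the only usable scan, and the last-assessment rule decides nothing.

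**Number affected, upper bound.** Control subjects × rejection rate:
- 2%: 0.02 × 120 = 2.4; 0.02 × 125 = 2.5
- 5%: 0.05 × 120 = 6; 0.05 × 125 = 6.25
- 10%: 0.10 × 120 = 12; 0.10 × 125 = 12.5

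These are ceilings, because they treat every rejected control scan as meeting the other three conditions.

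**Dilution of the between-arm difference.** Let r be the share of control scans replaced by a post-crossover repeat, and f the fraction of the full effect reached by then. For a true difference D, the control mean shifts by r × f × D, leaving D × (1 − r × f). Both r and f are assumptions.

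| r | Loss if f = 0.25 | Loss if f = 1 |
|---|---|---|
| 2% | 0.5% | 2% |
| 5% | 1.25% | 5% |
| 10% | 2.5% | 10% |

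**The case against.** The strongest reply is that the Protocol Summary, and likewise the COL definition in Protocol 17.8, place crossover after the Week 12 assessments are complete. The hand MRI is one of those assessments. A scan that has to be repeated can fairly be called incomplete, in which case crossover waits and the problem disappears. That reading is tenable. But 11.6.1 ties re-registration only to the MRI, and the schedule puts crossover at the Week 12 visit itself, so sites could reasonably act either way.

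Other points also stand. Subjects may choose options other than active stimulation. RAMRIS is exploratory and outside the Hochberg family. The long-term analysis is descriptive.

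A reader might infer three stronger things that the documents do not support:
- *That sham scans are in fact being acquired on active stimulation.* No rejection rate is given, several conditions must coincide, and stimulation is suspended for each scan.
- *That Titration 4, at day 91 ± 2, shows crossover is meant to proceed without a hold.* It does not. With a first scan on days 77 to 84, the repeat is due by days 84 to 91, and re-registration after that repeat can still be followed by Titration 4 on days 89 to 93. Only a first scan late in the window creates a conflict.
- *That the repeat necessarily becomes the Week 12 value.* That depends on how the visit is recorded, which the SAP leaves open.

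**Conclusion.** The gap is real but conditional. As written, the plan permits a control subject's Week 12 RAMRIS score to come from a repeat scan acquired after up to about 7 days of daily active stimulation. This requires a rejected scan, a choice of active stimulation, re-registration before the repeat, and the repeat being logged under Week 12.

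The likely size is small: at most about 2 to 12 of 120 to 125 controls at an assumed rejection rate of 2% to 10%. The loss of between-arm difference cannot exceed the share of control scans replaced, and is probably well below it after so short an exposure. If active stimulation improves the MRI measures, the bias is toward no difference, so it would not manufacture a benefit.

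The reach is limited to the exploratory Week 12 RAMRIS endpoints and the COL MRI baseline in CLP-008. ACR20 and the key secondary endpoints do not use MRI. The point merits a rule fixed before the primary dataset is locked, so that nobody has to choose scan by scan once assignments are known.

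**What to change.** **SAP 5.8.2 and 8.6.1.** State that Week 12 RAMRIS uses the last acceptable scan acquired on or before MicroRegulator re-registration, applied identically in both arms. Scans after re-registration are treated as missing for the Week 12 analysis and are not used as the COL baseline in CLP-008. Add a sensitivity analysis that includes them. The cut-off date is already in use: SAP 5.8 substitutes the re-registration date when the Week 12 visit date is missing.

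The rule has to cover both arms. Dropping late repeats in controls only would let treated subjects keep theirs and make missingness depend on assignment.

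The same sentence should say how these missing values enter the erosion progression rate, because SAP 5.8.1 counts missing binary outcomes as failures.

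**Protocol.** Section 4, Section 11.6.1 and Section 12.4 must be reconciled on whether a Week 12 MRI that awaits quality check or repeat counts as a completed assessment before re-registration. Which way to settle it is for the sponsor.

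**Cost.** A short addition to the SAP, one extra sensitivity table, and a few missing exploratory values. Sample size, power and alpha do not change.
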